3.3.3 Sampling Scheme

3.3.3.1 Sample Size

The student investigator calculated the sample size with the formula for two group comparison of means, exposed and unexposed groups for Cohort studies³⁶ by Epi-Info® -7 software. The outcome of the project is considered as a success if the difference between the intervening and comparison group in the first follow-up (O_1) assessment is 15% improvement in the patient-physician relationship percent score. From the existing literature of the other studies,³⁵ we assumed the baseline percent score of the patient-physician relationship to be 55.71% for both groups. After the intervention, the patient-physician relationship percent score is expected to increase to 64.07% in the intervention group in the first follow-up assessment (O_1).

The sample size is calculated based on the expected changes in the mean patient-physician relationship percent score in the intervention group of 15%. For variance, student investigator assumed that in both groups it will be equal. From a similar type of study,³⁵ the standard deviation of 2.5 was taken for calculation. Hence, the sample size was calculated to be one thousand one hundred and ninety eight (1198) in the intervention group and one thousand one hundred and ninety eight (1198) in the control group.

$$n_1 = n_2 = \frac{(Z\alpha/2 + Z\beta)^2 (\sigma_1^2 + \sigma_2^2)}{\Delta^2}$$

$$1198 = \frac{(1.96 + 1.28)^2 (2.5^2 + 2.5^2)}{(0.585)^2}$$

The literature shows that the response rate for similar types of evaluation studies have a response rate of 95%. Taking into consideration this information the estimated the sample size should be one thousand two hundred and sixty-two (1262) in each group.

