3.3.1 Measurable Objectives

- A month after the end of the program (December, 2015), the Patient-Physician Relationship percent score of the physicians' patients will increase by 15% compared to the baseline percent score of the intervention group (August 2015).³⁵
- Six months after the first follow-up assessment (June 2016), the Patient-Physician Relationship percent score of the physicians' patients will increase by 17% compared to the baseline percent score of the intervention group (August 2015).³⁵
- Six months after the first follow-up assessment (June 2016), the Patient-Physician Relationship percent score of the physicians' patients of the intervention group will be higher by 10% compared to the comparison group.³⁵

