3.3.5 Analysis

Once the supporting staff collects the data from survey participants, data entry will be carried out. In order to reduce the errors during the data entry, there will be cross checking of entered data by the project coordinator. The patient-physician relationship score from the questionnaire will be calculated into patient-physician relationship percent score.

Exploratory analysis will be done to clean the data by finding the missing values, outliers, and distribution of variables. Analysis will include descriptive analysis, independent T-test for continuous variables, Chi Square (χ^2) test for dichotomous variables, bivariate linear regression analysis and multivariate linear regression analysis.

4. Timeline

The proposed pilot project is planned to run for fourteen months, starting from June 2015 until August 2016. The physician leadership development program will be conducted for two months in the month of September and October 2015. The evaluation process will be conducted in three different duration, for baseline (O_0) and follow-up (O_1), (O_2) assessments (Appendix 5).

5. Budget

The total budget is estimated to be six million seven thousand eight hundred Armenian Drams (6,007,800.00 AMD) to implement this grant proposal (Appendix 6). The estimated budget for this grant proposal is calculated based on optimal fixed and overhead costs. The office and classroom for the program implementation, the classroom of 18 seating capacity is considered as an optimal. The rents are calculated as per AUA facilities' rental fees.⁴⁰ The costing is calculated for this proposal according to the average salaries for the personnel and type of services performed paid in the Armenian market as per May 2015.

6. Ethical Considerations

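### The success rule (Heratsi vs Muratsan at the first follow-up) is not among the measurable objectives, and on the stated targets the two can give opposite verdicts

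*Protocol*

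**What the plan says.** The surveys are O0 (August 2015), O1 (December 2015) and O2 (June 2016), each on independent samples of patients at Heratsi (intervention) and Muratsan (comparison).

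Protocol 3.3.3.1 Sample Size holds the only definition of project success: "The outcome of the project is considered as a success if the difference between the intervening and comparison group in the first follow-up" is a 15% improvement. The section uses a formula for comparing two group means. It then bases the size on the 15% change expected within the intervention group, from 55.71% to 64.07%.

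Protocol 3.3.1 Measurable Objectives sets three targets:

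- at O1, the patients' score "will increase by 15% compared to the baseline percent score of the intervention group";
- at O2, the score "will increase by 17% compared to the baseline percent score of the intervention group";
- at O2, the score "of the intervention group will be higher by 10% compared to the comparison group".

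Protocol 3.3.2 Evaluation Study Design describes the groups as non-equivalent and accepts that selection bias is possible. It relies on the comparison group to deal with history and maturation. Protocol 3.3.5 Analysis lists methods without tying any of them to an objective: "Analysis will include descriptive analysis, independent T-test for continuous variables", then chi-square tests and bivariate and multivariate linear regression.

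**The concern.** What the project must show to succeed is protocol content, and two sections state it differently. A final report written against 3.3.1 would never have to present the contrast that 3.3.3.1 says decides the matter. The first two objectives are uncontrolled before-and-after changes, so anything that lifts scores at both polyclinics counts fully towards them, although the design section brings in the comparison group to remove exactly that. If the two sections disagree once the data are in, the reader cannot tell which one governs, and the choice could be made after the results are known.

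**Working it through.** **1. What the percentages mean.** Section 3.3.3.1 assumes a baseline of 55.71% in both groups and expects 64.07% at Heratsi at O1. 55.71 × 1.15 = 64.07, so this figure reproduces, and 15% is a relative change (8.36 points). The targets are read the same way below.

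**2. Can the sections disagree?** The documents give no expected course for Muratsan, so its values here are assumptions.

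- Scenario A: Heratsi 55.71 → 64.07 → 65.18 (+15%, then +17%); Muratsan 55.71 → 59.05 → 59.05 (+6% at both follow-ups).
- Scenario B: Heratsi 55.71 → 64.07 → 60.17 (+15%, fading to +8%); Muratsan flat at 55.71.

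| Criterion | Target | Scenario A | Scenario B |
|---|---|---|---|
| Objective 1: Heratsi O1 vs O0 | +15% | +15%, met | +15%, met |
| Objective 2: Heratsi O2 vs O0 | +17% | +17%, met | +8%, missed |
| Objective 3: Heratsi vs Muratsan at O2 | +10% | 65.18/59.05 − 1 = 10.4%, met | 60.17/55.71 − 1 = 8.0%, missed |
| Success rule: Heratsi vs Muratsan at O1 | 15% | 64.07/59.05 − 1 = 8.5%, missed | 64.07/55.71 − 1 = 15.0%, met |

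Measured in points, the O1 gap in Scenario A is 64.07 − 59.05 = 5.02 against 8.36, so the success rule is still missed.

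**3. How wide is the range?** Let Heratsi reach its targets exactly and Muratsan rise by a fraction m at both follow-ups. Objective 3 needs 1.17/(1 + m) ≥ 1.10, so m ≤ 6.4%. The success rule needs 1.15/(1 + m) ≥ 1.15, so m ≤ 0. Every steady Muratsan rise above 0 and up to 6.4% meets all three objectives and fails the success rule.

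**4. What the uncontrolled objectives absorb.** In Scenario A, Muratsan gains 59.05 − 55.71 = 3.34 points without the programme. If that trend is common to both polyclinics, it supplies 3.34 of Heratsi's 8.36-point gain under objective 1. For a significance test, the protocol's SD of 2.5 and 1198 per group give a standard error of 2.5 × √(2/1198) = 0.102 points. A drift of 3.24 × 0.102 = 0.33 points would then make a within-Heratsi change significant about 90% of the time with no programme effect. With an assumed SD of 25 the drift needed is 3.3 points.

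**5. Error rate if any of the four contrasts were tested and claimed.** This applies only under a rule that the protocol does not state. With six independent samples of equal size, contrasts that share a sample correlate at 0.5 and the others at 0. Simulation under no effect gives a 16.7% chance of at least one two-sided p < 0.05 among the four (1 − 0.95⁴ = 18.5% if they were independent), and 13.0% for the three objectives alone. Counting only false benefit, the figures are 8.5% and 6.5%, against 2.5% for a single test.

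A separate matter: the printed formula gives (1.96 + 1.28)² × 12.5/0.585² = 383.4, so 384 per group and not 1198. Nothing in steps 1 to 3 depends on this.

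**The case against.** *Only 3.3.3.1 speaks of success, so there is one rule and the objectives are merely aims.* This stands in part: no section says that meeting an objective makes the project a success. But the deciding contrast is then missing from the list of what will be measured, and 3.3.3.1 itself moves from a between-group difference to a within-group change.

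*If Muratsan stays at baseline, objective 1 and the success rule coincide.* That is true under the equal-baseline assumption, but the protocol nowhere states that Muratsan stays flat. Met exactly, objectives 2 and 3 together imply a Muratsan rise of 1.17/1.10 − 1 = 6.4% by O2.

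*This is a pilot, and an analysis plan may settle the hierarchy.* Ranking of tests and division of alpha can indeed sit in a plan that is not shown, so their absence is no part of this point. The Executive Summary also gives regression the role of controlling confounders, which hints at the deciding model. None of this removes a conflict between two protocol sections.

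*The stronger reading.* A reader might infer that the plan carries a false-positive rate of about 17%. The documents do not support that. The value 1.96 appears only in the sample-size formula, for one comparison. The objectives are target sizes with no test attached. About half of the 17% is significant worsening. If the target sizes are the criteria, reaching one by chance is negligible: even with an assumed SD of 25, the smallest target (10% of 55.71 = 5.57 points) is about 5.5 standard errors at 1198 per group.

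**Conclusion.** The point holds as an inconsistency between 3.3.1 and 3.3.3.1 that can reverse the conclusion. With Heratsi exactly on target, any steady Muratsan rise above zero and up to 6.4% meets every objective and fails the success rule; a gain that fades by O2 does the opposite on the O2 objectives. This rests on relative percentages, equal baselines and assumed Muratsan values. It also rests on reading the criteria as target sizes, which is how the protocol writes them. If success meant p < 0.05 instead, Scenario A would show no conflict: its 5.02-point O1 gap is about 49 standard errors with SD 2.5 and about 4.9 with SD 25. So the disagreement example and the 17% belong to different readings and should not be added together. The 17% (8.5% for false benefit) is conditional on an any-of-four claim rule that the protocol does not contain, and on no trend, no baseline difference and independent patients. The point should be acted on before the data are seen.

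**What to change.** State the same single success criterion in 3.3.1 and 3.3.3.1: the Heratsi vs Muratsan contrast at O1. Add it to the objectives and say what the 15% is a percentage of. In 3.3.5, estimate it by the adjusted linear regression and include the O0 surveys of both polyclinics, so that a baseline difference between non-equivalent groups is not taken for an effect. Make the O2 between-polyclinic contrast secondary, tested only after O1 succeeds. Report the within-Heratsi changes and the unadjusted t-test and bivariate results as descriptive, with 95% confidence intervals and no success claim.

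The cost is a few sentences, with no extra patients or surveys. Within-Heratsi changes can no longer be claimed as success on their own, and O2 cannot be claimed if O1 fails. Using O0 costs precision: for a full difference in changes with equal independent samples, the standard error rises by √2, from 0.102 to 0.144 points with SD 2.5 and 1198 per group. Even with an assumed SD of 25 it would be 1.44 points, small against the planned 8.36.

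### The stated success threshold (a 15% between-group difference at O1) equals the assumed true effect and is not one of the listed objectives

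*Protocol*

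**What the plan says.** Section 3.3.3.1 (Sample Size) gives a success rule for O1, which begins: "The outcome of the project is considered as a success if the difference between the intervening and comparison group in the first follow-up". The size required there is a 15% gain in the score. The planning values follow: "we assumed the baseline percent score of the patient-physician relationship to be 55.71% for both groups", and after the training "the patient-physician relationship percent score is expected to increase to 64.07% in the intervention group in the first follow-up assessment". The section then says "The sample size is calculated based on the expected changes in the mean patient-physician relationship percent score in the intervention group of 15"%. The printed formula contains "1.96 + 1.28)^2 (2.5^2 + 2.5^2" over 0.585 squared, and the section states 1,198 per group, or 1,262 after a 95% response rate.

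Section 3.3.1 (Measurable Objectives) lists three targets:
- At O1, the score "will increase by 15% compared to the baseline percent score of the intervention group".
- At O2, the same within-group comparison with 17%.
- At O2, the score of the "patients of the intervention group will be higher by 10% compared to the comparison group".

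Section 3.3.5 (Analysis) names t-tests, chi-square tests and linear regression. It applies no 15% threshold.

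**The concern.** A sample-size formula with a z-beta term gives the probability of rejecting zero difference when the true difference equals the planning effect. It does not give the probability that the estimate reaches the planning effect. If the project is judged by whether the estimate reaches 15%, and 15% is also what it is expected to achieve, the sample size cannot raise the chance of success above about one half.

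The rule also stands apart from the objectives. The contrast that sizes the study and defines its success is absent from section 3.3.1, and nothing ranks it against the three targets listed there. One set of results could be called a success under one section and a failure under the other, and the choice could be made after the data are seen.

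**Working it through.** **1. The plan's own figure.** Inputs from section 3.3.3.1: z-values 1.96 and 1.28, SD 2.5 in both groups, difference 0.585.

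- Formula as printed: (1.96 + 1.28)² × (2.5² + 2.5²) / 0.585² = 10.4976 × 12.5 / 0.342225 = 383.4, so 384 per group.
- The stated 1,198 is not reproduced. Multiplying the variances instead of adding them gives it: 10.4976 × (6.25 × 6.25) / 0.342225 = 1,198.2.
- Non-response: 1,198 / 0.95 = 1,261.05, so 1,262, as stated.

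The sample-size arithmetic is a separate error. It matters here only because it fixes which power figure applies.

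**2. Threshold against assumed effect.** 64.07 / 55.71 = 1.150, a difference of 8.36 points. With the comparison group at 55.71%, the threshold is 0.15 × 55.71 = 8.36 points. The two are the same.

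**3. Chance of meeting the rule, read literally.** P(observed ≥ threshold) = 1 − Φ((threshold − true difference) / SE). With threshold equal to true difference this is 1 − Φ(0) = 50% for any n and any SD. The rounding in 64.07 moves it only slightly: at n = 1,198 it is 50.1% if the SD is 35.7 points (2.5 on an assumed 7-point scale, 2.5/7) and 51.4% if the SD is 2.5 points. If the comparison group also improves while the intervention group reaches 64.07%, the chance falls below 50%.

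**4. Power against zero, for contrast.** SE = 2.5 × √(2/n). This takes 0.585 as the 15% effect on the same scale as the SD of 2.5, and ignores clustering by physician.

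| n per group | SE | 0.585/SE − 1.96 | Power |
|---|---|---|---|
| 384 | 0.180 | 1.28 | 90.0% |
| 1,198 | 0.102 | 3.77 | 99.99% |

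**5. The targets side by side.**

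| Section | Time | Comparison | Target |
|---|---|---|---|
| 3.3.3.1 | O1 | between groups | 15% |
| 3.3.1 | O1 | within intervention group | 15% |
| 3.3.1 | O2 | within intervention group | 17% |
| 3.3.1 | O2 | between groups | 10% |

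The first row has no counterpart in section 3.3.1. With equal baselines, the two O2 targets together imply a comparison-group rise of 1.17/1.10 − 1 = 6.4%; the O1 planning values imply none.

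**6. If the criterion becomes a difference in change from O0 to O1.** Each wave is an independent sample (sections 3.3.2 Study Settings and 3.3.2 Evaluation Study Design), so the variance doubles: SE = 2.5 × √(4/n).

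- n = 1,198: SE 0.1445; 0.585/0.1445 − 1.96 = 2.09; power about 98%.
- n = 384: SE 0.255; 0.585/0.255 − 1.96 = 0.33; power about 63%.
- For 90%: 2 × 383.4 = 766.9, so 767 per group per wave.

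**The case against.** The sentence stands in the sample-size section next to the planning means, does not say that the observed difference must be at least 15%, and is not carried into section 3.3.5. It may be a loose statement of the effect to detect. That is fair, and on that reading the 50% does not apply. The sentence nevertheless defines success, so the wording needs correcting either way.

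Three stronger conclusions are tempting, and the protocol does not support them.

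- A reader might infer that the chance of success is 50% where the plan delivers 90%. The 90% is only nominal: it is what 1.28 would give at 384 per group. The planned 1,198 gives about 99.99% against zero on the protocol's inputs.
- A reader might infer that the 10% and 15% between-group figures contradict each other. They refer to O2 and O1. They are unaligned, not contradictory. With equal baselines and an unchanged comparison group, the 15% within-group and 15% between-group figures at O1 are even the same 8.36 points.
- A reader might try to state how far above 15% the true effect must lie for a 90% chance of meeting the threshold. At n = 1,198 this is about 15.2% if the SD of 2.5 is in percentage points, and about 18.4% if it sits on a 7-point scale with a baseline of 3.9. That scale is inferred (3.9/7 = 55.71%, 0.585/3.9 = 15%) and is not stated, so no single figure can be given.

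Wanting a minimum worthwhile effect is also legitimate in a pilot. At 1,198 per group, an interval-above-zero rule would accept an observed O1 contrast of 1.96 × 0.102 = 0.20, about a third of 0.585. A threshold above zero can be kept if it lies below the planning effect and the study is sized for it.

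**Conclusion.** The point holds in this form. The success rule in section 3.3.3.1 sets the threshold at the assumed true effect. As a rule on the observed difference it gives about a 50% chance of success under the plan's own assumptions. That figure rests on four conditions: 15% is relative (as 64.07/55.71 shows), the comparison group stays at 55.71%, the estimate is symmetric about its true value, and the sentence is taken literally. It needs no assumption about n, SD or scale. If the sentence only names the effect to detect, the fault is its wording.

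On both readings the objectives omit the between-group contrast at O1 that defines success. This is a defect in a stated decision rule. It does not show that the study as planned lacks power to detect the assumed effect.

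**What to change.** 1. In section 3.3.3.1, label 15% as the planning effect and remove it as the condition for success.
2. State one primary success criterion in identical words in sections 3.3.1 and 3.3.3.1. One option is that the two-sided 95% confidence interval for the Heratsi-minus-Muratsan contrast at O1 lies above zero.
3. Report the within-group 15% and 17% targets and the 10% between-group target at O2 as secondary estimates with confidence intervals.
4. Say whether the contrast is the O1 difference or the difference in change from O0 to O1, and restate size and power for it. The protocol itself names selection as a threat, which favours using the baseline wave.

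Cost: at the planned 1,198 per group per wave, wording in two sections and no extra patients under either contrast (about 99.99% or 98% power, ignoring clustering). If the sample size is corrected to what the printed formula gives, the choice matters: 384 gives 90% for the O1 difference but about 63% for the difference in change. The latter needs about 767 per group per wave, or 767/0.95 = 807.4, so 808 approached.

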3.3.4 Variables

The dependent variable of interest is Patient-Physician Relationship percent score, which is a numerical continuous outcome variable (Table 2). It is measured through 25 questions. The response options for each statement consists of nine levels of agreement between “Strongly Disagree” to “Strongly Agree”. The patient-physician relationship score ranging from 25-225 from the questionnaire will be re-calculated to patient-physician relationship percent score ranging from 11% to 100%.

The main independent variable of interest is being from Heratsi (intervention) or Muratsan (comparison) polyclinics. It is a nominal dichotomous type of variable. The special identification number of the questionnaire will identify the information.

The control variables suggested by literature include: participant’s sex, age, socio-economic status, educational status, and marital status.^{31,35,38,39} Literature shows that the above-mentioned control variables can influence the desired outcome of variable.^{31,35,38,39}

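### The sample-size equation mixes an unlabelled difference of 0.585 and SD of 2.5 with a planned percent-score difference of 8.36 points, and it evaluates to 384 per group, not the printed 1198

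*Protocol*

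**What the plan says.** Section 3.3.3.1 (Sample Size) states the effect on the percent score. For the start, "we assumed the baseline percent score of the patient-physician relationship to be 55.71% for both groups". At the first follow-up, "the patient-physician relationship percent score is expected to increase to 64.07% in the intervention group". Both groups are given the same variance: "the standard deviation of 2.5 was taken for calculation", from a cited study, with no unit.

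The equation has "1.96 + 1.28)^2 (2.5^2 + 2.5^2" in the numerator and the square of 0.585 in the denominator. Its result is printed as "one thousand one hundred and ninety eight (1198) in the intervention group", and the same for the control group. Because "similar types of evaluation studies have a response rate of 95" per cent, this is raised to "one thousand two hundred and sixty-two (1262) in each group".

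The outcome is defined in section 3.3.4 (Variables). Twenty-five items with nine response levels give a raw score of 25 to 225, which "will be re-calculated to patient-physician relationship percent score ranging from 11% to 100" per cent. Section 3.3.3.2 (Sampling Scheme) carries 1,262 into the fieldwork as about 64 surveys a day for 20 days, but obtains the sampling interval by dividing the number of visitors by nine. Appendix 6 (Budget) pays for 1018 completed questionnaires and costs data entry for 1080.

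**The concern.** The difference described in the text (8.36 points) is not the number in the equation (0.585), and nothing explains how one became the other. The SD cannot be judged against the outcome without a unit. The equation also does not equal the result printed beside it.

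A sample size that cannot be traced to the outcome being analysed gives no basis for deciding how many patients to survey. The decision matters here because the same document plans for 1,262 per group per wave in one place and for roughly 180 in two others. If the field team has to choose between them, the present calculation cannot tell them what is enough.

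**Working it through.** **Inputs** (section 3.3.3.1 unless noted): z values 1.96 and 1.28, that is two-sided 5% and 90% power; difference 0.585; SD 2.5 in both groups; means 55.71% and 64.07%; response rate 95%; percent score from 11.11% (25/225) to 100% (section 3.3.4).

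**1. The plan's own figure.** n = (1.96 + 1.28)² × (2.5² + 2.5²) / 0.585² = 10.4976 × 12.5 / 0.342225 = 383.4, so 384 per group. The printed 1198 is 3.1 times this. The value 1198 appears if the two variances are multiplied instead of added: 10.4976 × (6.25 × 6.25) / 0.342225 = 1198.2. That is a likely origin of the figure, but the document does not say so. The inflation step is right: 1198 / 0.95 = 1261.05, so 1262. Applied to 384 it gives 404.2, so 405.

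**2. Where 0.585 comes from.** 3.9 / 7 = 55.71%; 4.485 / 7 = 64.07%; 0.15 × 3.9 = 0.585. Of the scale maxima from 5 to 10, only 7 turns 8.36% into 0.585 (0.0836 × 7 = 0.585). A nine-level item would give 0.0836 × 9 = 0.752. The 7-point scale is therefore inferred from the arithmetic; the document names none.

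**3. The SD on the outcome's scale.** If 2.5 is on the same 7-point scale, it is 2.5 / 7 = 35.7 percent points. For comparison:
- uniform spread over the score range: (100 − 11.1) / √12 = 25.7;
- largest SD possible at a mean of 55.71: √[(100 − 55.71)(55.71 − 11.11)] = 44.4, reached only if every patient scores at one end or the other.

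So 35.7 exceeds the uniform spread and is 35.7 / 44.4 = 80% of the maximum.

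**4. n per group for 8.36 points**, n = 10.4976 × 2 × SD² / 8.36², independent patients, before non-response:

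| SD (percent points) | Basis | n per group |
|---|---|---|
| 15 | assumed | 68 |
| 20 | assumed | 121 |
| 25.7 | uniform spread | 199 |
| 35.7 (250/7) | 2.5 on a 7-point scale | 384 |
| 44.4 | maximum possible | 593 |

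With 1198 per group at SD 44.4, the standard error is 44.4 × √(2/1198) = 1.81 and 8.36 / 1.81 − 1.96 = 2.65, so power is about 99.6%.

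**5. The number against the fieldwork and budget.** Two groups and three waves at 1,262 need 6 × 1,262 = 7,572 questionnaires. An interval of visitors divided by nine yields nine patients a day, and 9 × 20 = 180 per group per wave, or 6 × 180 = 1080 in all. That is the data-entry figure in Appendix 6 (1080 × 5 minutes = 90 hours). The 1018 paid questionnaires are 1018 / 6, about 170 per group per wave. In the table, 170 to 180 is enough at SD 20, short at 25.7 and under half of what is needed at 35.7.

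**The case against.** The strongest reply is that nothing is lost. The planned 1198 exceeds what any SD possible on this scale at that mean would need, so the study cannot be short of power. Under independence this stands, and a reader who infers from the faulty equation that the trial is underpowered goes further than the document allows. But 1198 is not a margin that anyone planned. It is not the value of the printed expression, and neither the sampling interval nor the budget provides for it.

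A second reply is that a difference written on another scale is not itself an error. This also stands. If 0.585 and 2.5 share a scale, their ratio of 0.234, and hence 384, is the same in any unit. What remains is that the scale is not named and that an SD from another instrument may not carry over to a 25-item total.

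A reader might also take 2.5 as percent points and set it against 8.36, which gives 10.4976 × 12.5 / 69.89 = 1.88, or 2 per group, and conclude that the required number could be anything from 2 to 384. The document does not support that. The equation pairs 2.5 with 0.585, so a common scale is the natural reading, and an SD of 2.5 points on an 11 to 100 score is implausibly small.

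Finally, the judgement that 35.7 is doubtful rests on the bounds of the scale and not on data. The cited source of the SD is not at hand, so its unit cannot be settled here.

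**Conclusion.** The concern holds as an error of units and arithmetic in section 3.3.3.1. The inputs as printed give 384 per group (405 with non-response), not 1198 (1262), an overstatement of about 3.1 times. The difference and SD are not expressed on the outcome that will be analysed, and on the most coherent reading the SD is doubtful for that outcome. The 1,262 is also inconsistent with the interval in section 3.3.3.2 and with Appendix 6.

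The direction is toward oversizing and survey burden, not lost power. That conclusion assumes independent patients, as the protocol's formula does. Patients of the same physician may give similar scores; clustering would raise every n in the table, and the protocol gives no figure from which to say by how much. The 7-point origin is an inference, and the SDs of 15 and 20 are assumed values. The gap between 384 and 1198, and the conflict with the interval and budget, do not depend on either.

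**What to change.** 1. In section 3.3.3.1, state the difference (8.36) and the SD in percent-score points, and name the scale on which the source reported the SD and how it was converted.
2. Correct the printed result to 384 per group (405 after non-response), or justify another n. Print n for SDs of 15, 20, 25.7 and 35.7 (68, 121, 199, 384, no clustering) so the dependence on the SD is visible, and fix the number for the baseline wave.
3. Bring the daily target and divisor in section 3.3.3.2 and the questionnaire counts in Appendix 6 into line with the chosen n. At 405 per group per wave this means 405 / 20, about 21 a day, and 6 × 405 = 2,430 questionnaires.
4. After the baseline assessment (O₀) and before the first follow-up (O₁) in December 2015, recompute n for both follow-ups from the pooled baseline SD of the actual questionnaire. Appendix 5 already schedules data entry in August and analysis in September 2015. Baseline data precede the training and carry no treatment effect, so this has no cost in error rate. Each wave surveys new patients, so the follow-up numbers can be set separately.
5. Add a within-physician correlation to that recalculation only if a physician code is built into the questionnaire ID before August 2015. The present six-character ID records polyclinic, wave and participant number, and the form does not identify the physician.

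The cost is one rewritten paragraph, one recalculation from data already being collected, and matching edits to the sampling section and budget. At the budgeted 150 AMD per questionnaire, 2,430 would cost 364,500 AMD against the 152,700 now shown, while 7,572 would cost 1,135,800. The physician code is a small added cost in printing and handling the forms.
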